In renal transplant recipients, complete avoidance of calcineurin inhibitors from the time of renal transplant surgery has been associated with increased incidence of acute cellular rejection. Conflicting data is available regarding the impact of CI avoidance on long term renal allograft function.

We recently completed a retrospective analysis that evaluated renal transplant recipients in which calcineurin inhibitors have been substituted with sirolimus at 1 year post transplant and assessed the risk of rejection, patient and graft loss and renal allograft function. (Please see attached abstract submitted and accepted at the ATC 2007).

From this analysis we concluded that, in a prednisone-free regimen, the conversion from calcineurin inhibitors to sirolimus at 1 yr. post-transplant was not

associated with an increased risk of acute rejection or graft loss. A trend towards a better GFR was noted after conversion from calcineurin inhibitors to sirolimus.

Little is known of the impact of immunosuppressive changes post renal transplant on lymphocytes function.

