### **Research Objective**

The aim of the present study is to prospectively investigate the impact of CI conversion (tacrolimus→sirolimus) between 6 and 24 months post-transplant on the incidence of acute cellular rejection, renal allograft function and lymphocytes function.

Primary aim of the study is:

to investigate the impact of CI conversion (tacrolimus→sirolimus) on the incidence of acute cellular rejection.

Secondary aims of the study are:

- i) evaluate whether CI conversion (tacrolimus→sirolimus) contributes positively or negatively on the renal allograft function calculated with e-GFR and proteinuria;
- ii) patient and graft survival ;
- iii) evaluate if CI conversion impacts on lipid profile, incidence of hypertension, malignancies, and opportunistic infections and post-transplant DM;
- iv) evaluate possible modifications of lymphocytes function before and after conversion (tacrolimus→sirolimus)
- v) assess tubular toxicity by evaluating urinary biomarkers

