### **Randomization**

For this research study, between 6 and 24 months post-transplant we plan to prospectively randomize 2:1 renal transplant patients to either:

- Continue with tacrolimus and MMF or
- Substitute tacrolimus with sirolimus and continue MMF

A total of 400 pts. are expected to be screened for the randomization and we expect to be able to randomize 275 renal transplant patients into this protocol.

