## **Statistical Analysis**

Once the 2 groups of renal transplant patients are identified, two sample t tests will be used to compare differences in continuous variables between groups; chi square tests will be used to compare differences in discrete variables. Multivariable logistic regression analysis will be also performed to identify the combination of clinical variable that are significantly associated with the development of acute rejection and renal allograft function after conversion from tacrolimus →sirolimus.

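### The primary rejection comparison is a chi-square test with no effect estimate or interval, so a non-significant result would not show how much excess rejection has been ruled out

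*Combined protocol and SAP*

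**What the plan says.** The Research Objective section gives the primary aim as "to investigate the impact of CI conversion (tacrolimus→sirolimus) on the incidence of acute cellular rejection". It states no hypothesis or direction.

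The Background supplies the context. Avoiding calcineurin inhibitors altogether from the time of surgery "has been associated with increased incidence of acute cellular rejection". The sponsor's own retrospective series is then reported as finding that conversion at one year was not "associated with an increased risk of acute rejection or graft loss". No interval accompanies that statement.

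The Statistical Analysis section is one short paragraph. Continuous variables are compared by t tests, and for the rest "chi square tests will be used to compare differences in discrete variables". It continues: "Multivariable logistic regression analysis will be also performed to identify the combination of clinical variable that are significantly associated" with acute rejection and allograft function after conversion.

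On size, the Randomization section says "we expect to be able to randomize 275 renal transplant patients into this protocol", with a plan to "prospectively randomize 2:1 renal transplant patients to either" of the two regimens. No significance level, power, expected rejection rate, margin or time point is attached to the primary aim. The only power analysis mentioned is in the Biopsy section, for the biopsies, and its inputs are not shown.

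**The concern.** The trial replaces an established drug. The hoped-for gain is in renal function and the feared cost is rejection, so the useful primary result is how large an excess of rejection the data still allow. A chi-square p-value does not answer that. It says whether a zero difference is compatible with the data, and is silent on whether an excess of 5, 10 or 15 points is compatible as well.

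If rejection is uncommon, non-significance is a frequent outcome even when conversion does real harm. The plan prespecifies nothing to put beside the p-value, so a non-significant result could be reported as reassurance on the primary endpoint without showing what had been excluded.

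**Working it through.** **Inputs from the documents.** Total 275, allocation 2:1 (Randomization). The Biopsy section expects about 46 tacrolimus and 93 sirolimus subjects; 93/46 = 2.02, so sirolimus is the larger arm. These counts are used only for the direction of the ratio. Then 275/3 = 91.7, giving about 92 tacrolimus and 183 sirolimus.

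**Assumptions.** Two-sided 0.05; chi-square without continuity correction; tacrolimus rejection rates of 5%, 10%, 15% and 20%; no loss to follow-up unless stated. The 275 itself cannot be reproduced, because none of the quantities needed to derive it is given.

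**Step 1: chance of missing a doubling.** Let p be the tacrolimus rate, q = 2p the sirolimus rate and m = (92p + 183q)/275. With 1/92 + 1/183 = 0.016334:

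- s0 = √[m(1−m) × 0.016334]
- s1 = √[p(1−p)/92 + q(1−q)/183]
- power = Φ[(q − p − 1.96·s0)/s1]

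| p → q | m | s0 | s1 | argument of Φ | power | non-significant |
|---|---|---|---|---|---|---|
| 5% → 10% | 0.0833 | 0.0353 | 0.0318 | −0.605 | 27% | 73% |
| 10% → 20% | 0.1665 | 0.0476 | 0.0430 | 0.155 | 56% | 44% |
| 15% → 30% | 0.2498 | 0.0553 | 0.0503 | 0.826 | 80% | 20% |
| 20% → 40% | 0.3331 | 0.0602 | 0.0552 | 1.483 | 93% | 7% |

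With an assumed 20% loss (73 and 147 subjects), power falls to 22%, 46%, 69% and 86%.

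**Step 2: precision.** The 95% half-width for the risk difference at equal rates is 1.96 × √[p(1−p) × 0.016334]. It is 5.5, 7.5, 8.9 and 10.0 points at 5%, 10%, 15% and 20%. On this approximation, equal observed rates of 5% would just fail to exclude a doubling (5 points). At 10% and above they would exclude a doubling, but not a smaller excess within the half-width.

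**Step 3: what a just non-significant result leaves open.** Take 5/92 (5.4%) versus 24/183 (13.1%), a difference of 7.7 points. Chi-square = 3.83, p = 0.0504. The Wilson 95% limits are 2.34% to 12.10% and 8.97% to 18.77%. The Newcombe limits for the difference are:

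- lower: 7.68 − √[(13.11 − 8.97)² + (12.10 − 5.43)²] = 7.68 − 7.85 = −0.2 points
- upper: 7.68 + √[(18.77 − 13.11)² + (5.43 − 2.34)²] = 7.68 + 6.45 = +14.1 points

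The largest non-significant sirolimus counts against the other assumed rates behave the same way:

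| Tacrolimus | Sirolimus | p | Newcombe upper limit |
|---|---|---|---|
| 9/92 (9.8%) | 34/183 (18.6%) | 0.058 | 16.5 points |
| 14/92 (15.2%) | 46/183 (25.1%) | 0.060 | 18.9 points |
| 18/92 (19.6%) | 56/183 (30.6%) | 0.052 | 20.8 points |

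Each would be reported as not significant, although the upper limits run from 14.1 to 20.8 points.

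**The case against.** The best defence is that the aim is worded neutrally, as an impact. A two-sided test of difference is a conventional choice for such an aim, and the renal secondary aim explicitly allows either direction. That stands: the chi-square is not wrong as a test, and the documents do not declare a non-inferiority trial. A reader might infer that they do. The emphasis on excess rejection comes from the Background. It is supported by the Stopping Rules, which return a subject to tacrolimus after two rejections following conversion.

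The chi-square is also not the only analysis that touches rejection, since a logistic regression is listed and such models usually yield odds ratios with intervals. But this one is described as a search for significant associations after conversion. Treatment arm is not named as a term, and no treatment-effect estimate is promised. It does not fill the gap.

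A reader might further infer that the sponsor will treat non-significance as proof of safety. The plan contains no such rule. The wording about the retrospective series makes that reading plausible, but its abstract is not among the documents, so the basis of that conclusion cannot be seen.

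Finally, a reader might infer that the trial would probably miss a doubling. That holds at a 5% rate (73%). At 10% the chance is somewhat below even (44%), and at 15% to 20% a doubling would usually be detected. With no rate stated and four years of follow-up, no scenario is privileged.

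**Conclusion.** The concern holds as a fault in how the primary comparison is specified. The one between-arm analysis stated for the primary outcome is a test of difference, with no effect estimate or interval, and a non-significant result could be taken as no increase when a sizeable excess is not excluded. How often that situation would arise depends on a rejection rate the documents do not give: a true doubling is missed with probability from 73% (5% rate) down to 7% (20% rate). At all four rates the expected precision is only 5.5 to 10.0 points either way. The figures rest on 92 and 183 subjects, two-sided 0.05 and no losses; losses would worsen them. The documents do not support saying that the test is invalid, that a reading rule has been adopted, or that a doubling would be missed whatever the rate. The change should be made because it determines what the trial can conclude about its primary aim.

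**What to change.** Replace the bare test with this specification:

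- The primary result is the sirolimus-minus-tacrolimus difference in cumulative risk of acute cellular rejection, among all randomised subjects in their assigned arms, at one fixed time point within the four-year follow-up.
- It is reported with a 95% confidence interval by one named method, for example the Newcombe score interval.
- The chi-square test is kept as supportive.
- Any conclusion that conversion does not increase rejection rests on the upper confidence limit and not on a non-significant test.

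A prespecified margin is optional; the fix does not depend on one.

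The cost is one paragraph and no additional subjects. The analysis does need rejection status to the chosen time point for subjects who withdraw. The section on follow-up of withdrawn subjects commits only to attempting survival data as a minimum, so it should name rejection as well. The downside for the sponsor is that the conclusion may have to be worded less favourably.

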## **Safety and Adverse Events**

For the purpose of this clinical trial, the National Cancer Institute Common Terminology Criteria for Adverse Events v3.0 (CTCAE), dated December 12, 2003 will be used to grade all adverse events.

## **Definitions**

### **Adverse Event**

An **adverse event** (AE) is any symptom, sign, illness or experience that develops or worsens in severity during the course of the study. Intercurrent illnesses or injuries will be regarded as adverse events. Abnormal results of diagnostic procedures are considered to be adverse events if the abnormality:

- results in study withdrawal
- is associated with a serious adverse event
- is associated with clinical signs or symptoms
- leads to additional treatment or to further diagnostic tests
- is considered by the investigator to be of clinical significance

### **Serious Adverse Event**

Adverse events are classified as serious or non-serious. A **serious adverse event** is any AE that is:

- fatal
- life-threatening
- requires or prolongs hospital stay
- results in persistent or significant disability or incapacity
- a congenital anomaly or birth defect
- an important medical event

Important medical events are those that may not be immediately life threatening, but are clearly of major clinical significance. They may jeopardize the subject, and may require intervention to prevent one of the other serious outcomes noted above. For example, drug overdose or abuse, a seizure that did not result in in-patient hospitalization, or intensive treatment of bronchospasm in an emergency department would typically be considered serious.

All adverse events that do not meet any of the criteria for serious should be regarded as ***non-serious adverse events***.

### **Adverse Event Reporting Period**

The study period during which adverse events must be reported is normally defined as the period from the initiation of any study procedures to the end of the study treatment follow-up. For this study, the study treatment follow-up is defined as 30 days following the last administration of study treatment.

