### **Post randomization**

The recipients assigned to continue with tacrolimus and MMF will be routinely followed at our outpatient Transplant center with monthly labs. In addition to the baseline pre-randomization labs, at 6, 12 and 24 months post randomization, peripheral blood leukocytes will be obtained to study lymphocytes functional activity and to characterize lymphocytes subpopulations by flow cytometry analysis.

Post randomization, the recipients assigned to switch from tacrolimus to sirolimus and continue with MMF will be routinely followed at our Transplant center with monthly labs. Furthermore, during the period of conversion from tacrolimus to sirolimus, weekly labs will be obtained to monitor renal function and bone marrow function. In addition to the baseline pre-randomization labs, and labs collected at 6, 12, 24, 36, and 48 months post randomization, peripheral blood leukocytes will be obtained to study lymphocytes functional activity to characterize lymphocytes subpopulations by flow cytometry analysis and urine will be collected to assess tubular toxicity by evaluating urinary biomarkers.

Both groups of patients will be followed for 4 years post-randomization. In addition to monitoring renal allograft function, we will evaluate the incidence of acute rejection, patient and graft survival, the impact of CI conversion on the lipid profile, the incidence of hypertension, malignancies, opportunistic infections and post-transplant DM.

Furthermore, with the peripheral leukocytes obtained at baseline prior to randomization and at 6, 12, 24, 36, and 48 months post-randomization we will investigate possible modifications of lymphocytes function and of the lymphocytes subpopulations that might have occurred as a consequence of the switch from tacrolimus to sirolimus.

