## **Primary Safety Endpoints**

The primary safety endpoints will be assessed on the adverse events (AEs) and serious adverse events (SAEs) that are observed throughout the trial.

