## **Early Withdrawal of Subjects**

### **When and How to Withdraw Subjects**

Subjects may withdraw from the clinical trial at any time for any reason with no prejudice to their medical care. Subjects may also be stopped in the study without their consent if their medical care requires they be. Also, the Institutional Review Board (IRB) may stop the study at any time and all subjects will be returned to taking tacrolimus and followed for safety. Subjects will be informed of why they are being stopped.

Subjects non-compliant with medications and clinic follow-ups will be withdrawn from the study.

Subjects with post-transplant complications such as malignancy or infections that require modification or withdrawal of maintenance immunosuppression will be withdrawn from the study.

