### **Data Collection and Follow-up for Withdrawn Subjects**

Even though subjects may be withdrawn prematurely from the study, an attempt will be made to collect at least survival data on such subjects throughout the protocol defined follow-up period. Such data is important to the integrity of the final study analysis, since early withdrawal could possibly be related to the safety profile of the study. If a subject withdraws consent to participate in the study, attempts will be made to obtain permission to record at least survival data up to the protocol-described end of subject follow-up period.

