### **Stopping Rules**

Subjects diagnosed with two acute renal allograft rejection episodes post conversion from tacrolimus to sirolimus will be stopped from participating in the study and will be switched back to tacrolimus.

Subjects that develop significant side effects secondary to sirolimus (severe thrombocytopenia (platelets count <50, 000); severe hyperlipidemia not controlled by the use of statins or other cholesterol lowering agents; worsening proteinuria or severe de-novo proteinuria) will have sirolimus stopped and patients will be switched back to tacrolimus.

Subjects developing post-transplant infections (i.e., UTI, CMV, HSV, EBV, HCV, HBV, HIV, PCP), that in the opinion of the investigator are detrimental to the subject and their participation in this research trial, will be stopped from participating in this study.

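### Mandatory AE reporting ends 30 days after an undefined 'study treatment', although safety is to be assessed throughout a trial with 4 years of follow-up

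*Combined protocol and SAP*

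**What the plan says.** Primary Safety Endpoints rests the safety assessment on "adverse events (AEs) and serious adverse events (SAEs) that are observed throughout the trial". Post randomization sets the length of the trial for a subject: "Both groups of patients will be followed for 4 years post-randomization". It also lists outcomes to be evaluated in that time, among them "the incidence of hypertension, malignancies, opportunistic infections and post-transplant DM".

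Adverse Event Reporting Period defines when AEs must be reported: "the period from the initiation of any study procedures to the end of the study treatment follow-up". It then fixes the end of that period: "the study treatment follow-up is defined as 30 days following the last administration of study treatment". Recording of Adverse Events makes recording mandatory for AEs within the study period, so this definition governs what is collected.

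Two sets of rules determine who reaches the end of that window early.

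- Stopping Rules: converted subjects with two rejection episodes leave the study and return to tacrolimus. Those with listed sirolimus side effects "will have sirolimus stopped and patients will be switched back to tacrolimus", with no statement that they leave the study. Subjects in either arm with infections that the investigator judges detrimental leave the study.
- When and How to Withdraw Subjects, for both arms: non-compliant subjects are withdrawn, and "Subjects with post-transplant complications such as malignancy or infections that require modification or withdrawal of maintenance immunosuppression will be withdrawn from the study".

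For withdrawn subjects, Data Collection and Follow-up for Withdrawn Subjects says that "an attempt will be made to collect at least survival data on such subjects throughout the protocol defined follow-up period". It does not mention AEs.

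**The concern.** A safety endpoint assessed throughout the trial needs an observation period that does not depend on treatment. Here the period does depend on it, through a term with two defensible meanings that give different AE counts from the same patients.

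If subjects stop treatment or leave the study at different rates in the two arms, the arms are observed for AEs for different lengths of time. The planned analysis would not correct for this. Statistical Analysis names t tests, chi-square tests and logistic regression, and no person-time or exposure-adjusted method. The withdrawn-subject section itself accepts that early withdrawal may be linked to safety, so the unobserved time need not be a random part of the whole.

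**Working it through.** The documents give no expected discontinuation rate, AE rate or safety power, so there is no figure of the plan's to reproduce. The check is first textual, then an illustration on assumed rates.

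**Step 1: the two readings.** The Study drugs section lists sirolimus, MMF and tacrolimus, but nothing says which of them counts as 'study treatment' for the reporting window.

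- *Randomised drug only.* The clock starts when sirolimus stops. A subject switched back for side effects stays in the study, but mandatory AE reporting ends 30 days later.
- *All listed drugs.* A switch back to tacrolimus with MMF continued starts no clock. The loss is confined to subjects withdrawn from the study, for whom only an attempt at survival data, as a minimum, is promised. The two-rejection stop is one such route, and it applies to converted subjects only. The malignancy, infection and non-compliance routes apply to both arms.

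**Step 2: what later provisions still capture.** Post-study Adverse Event requires notification of deaths and AEs that may reasonably be related, at any time after participation ends. Recording of Adverse Events requires possibly related SAEs after the study period to be recorded, and ongoing SAEs to be followed to outcome. What remains without a collection requirement is non-serious AEs not judged related and SAEs judged unrelated. Relatedness is judged with treatment known, since all drugs are given open label.

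**Step 3: illustration, randomised-drug reading.** Inputs from the protocol: 275 subjects and 2:1 allocation (Randomization); 48 months of follow-up (Post randomization). The larger arm is taken as sirolimus from the biopsy counts of about 93 versus 46 (Biopsy).

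- Sirolimus: 275 × 2/3 = 183.3 subjects, × 4 years = 733 planned patient-years.
- Tacrolimus: 275 × 1/3 = 91.7 subjects, × 4 years = 367 planned patient-years.

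Let *d* be the proportion stopping and *t* the month of stopping (both assumed), with 1 month for the 30-day tail:

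share of AE time lost = *d* × (48 − *t* − 1)/48

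At *t* = 12 the factor is 35/48 = 0.729.

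- Sirolimus, *d* = 20%: 0.20 × 0.729 = 14.6%, about 107 of 733 patient-years.
- Tacrolimus, *d* = 5%: 0.05 × 0.729 = 3.6%, about 13 of 367 patient-years.

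If true AE rates are equal and constant, and events are counted per randomised subject, the observed sirolimus:tacrolimus ratio is (1 − 0.146)/(1 − 0.036) = 0.89.

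| Month of stopping | Stopping, sirolimus / tacrolimus (assumed) | AE time lost, sirolimus / tacrolimus | Observed ratio |
|---|---|---|---|
| 6 | 40% / 10% | 34.2% / 8.5% | 0.72 |
| 6 | 20% / 5% | 17.1% / 4.3% | 0.87 |
| 12 | 40% / 10% | 29.2% / 7.3% | 0.76 |
| 12 | 20% / 5% | 14.6% / 3.6% | 0.89 |
| 12 | 10% / 5% | 7.3% / 3.6% | 0.96 |
| 24 | 20% / 5% | 9.6% / 2.4% | 0.93 |
| 24 | 10% / 5% | 4.8% / 2.4% | 0.98 |
| 12 | 20% / 20% | 14.6% / 14.6% | 1.00 |

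The ratio departs from 1.00 only when stopping is unequal. With observed person-time as denominator and a constant rate, numerator and denominator shrink together and the ratio stays at 1.00. The protocol does not say which denominator will be used.

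**Step 4: after the change in the fix.** With collection to month 48 whatever the treatment, the time lost to the 30-day rule is 0 in both arms, before death, loss to follow-up or withdrawal of consent.

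**The case against.** The best defence is that the wider reading of 'study treatment' is at least as natural. Tacrolimus and MMF stand under Study drugs, MMF continues in both arms, and a subject who stops sirolimus for side effects returns to tacrolimus and is not said to leave the study. On that reading no clock starts. The outcomes named in Post randomization are planned over 4 years without reference to the AE window, so they do not lapse for subjects who remain in the study. Survival data is a minimum, not a limit. A 30-day on-treatment window is also an accepted safety convention.

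All of this stands, and it limits the point. It does not remove the conflict, because the protocol never chooses a reading and because AE collection after withdrawal is left open under either.

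A reader might go further and infer that late events are simply lost, mainly in the converted arm, so that sirolimus malignancy, infection and AE rates are understated against controls observed for the full 4 years. The documents do not support that:

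- Related late events remain reportable.
- The withdrawal rules and the infection stop also remove tacrolimus subjects, so controls are not all observed for 4 years.
- A malignancy or infection that triggers withdrawal arises while the subject is still in the study.
- No discontinuation rates are given for either arm.
- Understatement also requires all-randomised denominators, which the protocol does not specify.

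**Conclusion.** The point holds as a conflict between sections. Mandatory AE reporting is tied to an undefined 'study treatment', while the primary safety endpoints span the trial. On the randomised-drug reading, collection ends early for anyone who stops sirolimus. On the wider reading, it ends within 30 days for subjects withdrawn from the study. The uncollected events are non-serious AEs not judged related and SAEs judged unrelated.

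Converted subjects have more routes to this gap, because the two-rejection stop and the sirolimus side-effect rule apply only to them. Whether this produces an actual imbalance cannot be determined from the documents. The ratio of 0.89 rests on assumed stopping of 20% versus 5% at month 12, the randomised-drug reading, equal constant true rates and all-randomised denominators. Across the unequal-stopping scenarios run it lies between 0.72 and 0.98, and with equal stopping it is 1.00.

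This deserves more than a clarification of wording, because the change removes a treatment-dependent observation window from the safety comparison at low cost. No position is taken on the clinical stopping rules.

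**What to change.** 1. In Adverse Event Reporting Period, define AE and SAE collection as randomisation to month 48 for every randomised subject, whatever treatment is being taken, subject to continued consent and authorisation as described in Data Collection and Follow-up for Withdrawn Subjects and in Confidentiality.
2. Define 'study treatment', and keep the 30-day window only for a secondary on-treatment tabulation.
3. In Statistical Analysis, report AEs and SAEs by randomised arm with exposure-adjusted rates, stating the denominator.
4. Align Primary Safety Endpoints, Data Collection and Follow-up for Withdrawn Subjects, and Recording of Adverse Events with the new period, so that AEs as well as survival are sought after withdrawal.

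The cost is protocol wording plus some added AE collection after discontinuation, at a single transplant centre where both arms have routine follow-up with monthly labs. Data will still be incomplete where consent or authorisation is withdrawn, or where a subject no longer attends. The report should give the number of such subjects by arm.
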